4.10.3.4 Functional Independence Measure

The FIM (or WeeFIM for pediatric patients) assesses motor tasks (13 items) and cognitive tasks (5 items), each rated on a 7-point ordinal scale, with higher values denoting greater functional independence. The total score ranges from 18 (total assistance) to 126 (complete independence); the total subscores range from 13 to 91 for the motor component, and from 5 to 35 for the cognitive component. In the WeeFIM, the motor component is comprised of two domains: a self-care domain with 8 items (subscores ranging from 8 to 56) and a mobility domain with 5 items (subscores ranging from 5 to 35). If an item is missing, then the total score and corresponding subscore will not be computed.

A descriptive summary of the absolute change from baseline in motor and cognitive components of the scale, along with the total score, will be presented by treatment group, overall (pooled across age groups) and within each age group (pediatric, adult). For the pediatric group, the subscores for the self-care and mobility domains will also be summarized. In addition, at Week 24, categories for change from baseline FIM total score (e.g., <0, =0, >0, ≥1, ≥2, ≥3, ≥4), categories for percent improvement (i.e., increase) in

FIM total score from baseline (i.e., $<0\%$, $=0\%$, $>0\%$, $\geq 10\%$, $\geq 20\%$, $\geq 30\%$, $\geq 40\%$, $\geq 50\%$), and categories for FIM total score status (improvement, no change, or worsening) will be presented.

Frequency counts of the change from baseline score across each FIM item, as well as shift from baseline, will be presented for Week 24. Categories for change from baseline FIM item score (i.e., <0 , $=0$, >0 , ≥ 1 , ≥ 2 , ≥ 3 , ≥ 4), and categories for FIM item score status (improvement, no change, or worsening) will be presented, as well. In addition, frequency counts will be presented by treatment group for patient locomotion (walk, wheelchair or both), comprehension (auditory, visual, or both) and expression (vocal, nonvocal, or both) will be presented at baseline and Week 24.

A chi-squared test will be performed at Week 24 to determine treatment differences between the percentages of patients who had a total score indicating improvement, no change, or worsening. Proportions, with estimated 95% CI, will be reported for each treatment group, along with a p-value corresponding to the treatment comparison.

The change in FIM (or WeeFIM) total score from baseline to the Week 24 visit will be evaluated using an ANCOVA model, with treatment and age group (pediatric, adult) as fixed effects, and baseline score as a covariate, pooling data across age group (pediatric, adult). The model will be run using the observed case. The adjusted mean treatment difference will be reported together with its 95% confidence interval.

A by-patient listing will be provided, which presents FIM scores (total and for each component) across all assessments in the double-blind and open-label periods for patients in the Double-Blind FAS.

4.10.3.5 Function Measures

Ambulation: Patients able to attempt this assessment will have 2 trials to walk 25 feet, and the average time (in seconds) of these trials will be taken. Patients must successfully complete 2 trials in order for the assessment to have been considered completed. If there is only data available for 1 trial, for reasons other than a patient's inability to perform the test, then the time for the single, available trial will be considered as the average.

Descriptive statistics will be used to summarize average walking speeds (in seconds) at each study visit of the double-blind treatment period (Baseline, Weeks 6, 12, 18, and 24) for patients in the Double-Blind FAS, along with absolute and percent change from baseline for post-baseline visits. Categories for percent improvement (i.e., decrease) in average walking speed (in seconds) from baseline (i.e., $<0\%$, $=0\%$, $>0\%$, $\geq 10\%$, $\geq 20\%$, $\geq 30\%$, $\geq 40\%$, $\geq 50\%$), and categories for average walking speed (improvement, no change, or worsening) will be presented, as well. This table will be repeated using age group (pediatric, adult) as a subgroup.

Moreover, the walking speeds will be converted to z-scores, using the baseline values of patients in the Double-Blind FAS as reference values. The z-score conversion will follow the below formula:

(Observed value [in seconds] – average of all baseline values [in seconds]) / standard deviation of all baseline values [in seconds].

Then, the z-score will be adjusted (multiply z-score by -1) so that a higher z-score will correspond to a better speed (fewer seconds). For patients who are unable to complete the 25-foot walk test, a z-score will be imputed using the worst observed z-score across all patient visits.

Descriptive statistics of the z-score, including absolute and percent change from baseline, will be presented for patients in the Double-Blind FAS at each visit during the double-blind period. Depending on the number of patients with available data, the MMRM model (as described for the primary endpoint) will be used to evaluate the treatment effect on change from baseline walking speed z-score. The difference between adjusted treatment means will be reported, together with its 95% CI.

Frequency counts will be presented showing percentages of patients using given assistive devices at each visit, percentages of patients who failed to complete 1 or more trials, and percentages of patients in the Double-Blind FAS who reported a change in level of assistance needed.

In addition, figures will be presented which show the walking speed for each visit during the double-blind period, as well as change from baseline speed by treatment group. A by-patient listing will be provided, which presents the results from the 25-foot walk test (including Trials 3 and 4, if necessary) across all assessments in the double-blind and open-label periods for patients in the Double-Blind FAS.

Speech: Diadochokinetic test (DDK) assessments will provide 4 scores for analysis: three scores for the alternating motion rate (AMR) and one for the sequential motion rate or (SMR). For the three AMR scores, patients will be required to recite a single syllable (“puh”, “tuh”, and “kuh”) as rapidly as possible in one breath. The AMR will be derived as the number of repetitions over the duration (in seconds). For the SMR scores, patients will be required to recite multiple syllables (“puhtuhkuh”) as rapidly as possible in one breath. The SMR will be derived as the number of repetitions over the duration (in seconds).

The AMR and SMR will be analyzed using descriptive statistics at baseline and Week 24 of the double-blind period, including absolute and percent change from baseline.

Categories for percent improvement (i.e., decrease) in AMR/SMR (i.e., $<0\%$, $=0\%$, $>0\%$, $\geq 10\%$, $\geq 20\%$, $\geq 30\%$, $\geq 40\%$, $\geq 50\%$), and categories for AMR/SMR status (improvement, no change, or worsening) will be presented, as well. This will be repeated using age group (pediatric, adult) as a subgroup.

Moreover, for each score, the change from baseline to the Week 24 visit of the double-blind period will be evaluated using an ANCOVA model, with treatment and age group (pediatric, adult) as fixed effects, and baseline score as a covariate. The models will be run using observed cases. The adjusted mean treatment difference will be reported together with its 95% confidence interval.

For each of the 4 repetition tasks (“puh”, “tuh”, “kuh”, “puhtuhkuh”), the number of repetitions performed will also be summarized descriptively at baseline and Week 24 during the double-blind period. This will be repeated using age group (pediatric, adult) as a subgroup.

A by-patient listing will be provided, which presents the duration, repetitions, and repetition rates for the AMR and SMR across all assessments in the double-blind and open-label periods for the Double-Blind FAS.

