6.1.4. Exploratory Efficacy Endpoints

Exploratory efficacy endpoints will include change from Baseline to the end of the 24-week double-blind period in the following:

- Clinician Global Impression of Improvement (CGI-I)
- Barry Albright Dystonia (BAD) scale

- Quality of life (QoL):
 - Neuro-QoL, upper and lower extremity modules (adult and pediatric versions)
 - EuroQol 5-dimension, 3 level QoL instrument (EQ-5D-3L)/EuroQol-5D Youth Version (EQ-5D-Y)
- Functional independence: Functional Independence Measure (FIM)/Functional Independence Measure for Children (WeeFIM)
- Function measures:
 - Ambulation: 25-foot walk test (in appropriate patients)
 - Speech: Diadochokinetic (DDK) assessments (ie, alternating motion rate [AMR] and sequential motion rate [SMR])

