Hypothesis-testing will be performed at the two-sided 5% significance level, unless otherwise stated.

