4.2 Determination of Sample Size

It is estimated that a total of 74 patients (37 in each treatment group) will provide approximately 80% power to detect a 3-point difference between groups in the average change from baseline score for the PKAN-ADL, based on Student's t-test with alpha=0.05 (two-sided); this calculation assumes a standard deviation of 4.5 points for the change from baseline scores. Allowing for 10% attrition, a total of 82 patients will be randomized to achieve the target sample size of at least 74 patients completing the double-blind period of the study.

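### The walk-test status table in seconds files patients who lose the ability to walk under missing, not under worsening

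*SAP*

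**What the plan says.** SAP 4.10.3.5 reports the 25-foot walk in two ways.

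**In seconds.** The value is the average of two trials. "Patients must successfully complete 2 trials in order for the assessment to have been considered completed". A single available trial may stand in for the average, but not when the other is absent because the patient could not perform the test. From this average the SAP derives descriptive statistics at Baseline and Weeks 6, 12, 18 and 24, absolute and percent change, and percent-improvement bands; in addition, "categories for average walking speed (improvement, no change, or worsening) will be presented, as well". Nothing says how to treat a visit at which the patient is unable to complete the test.

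**As a z-score.** Times are standardised to the Baseline values of the Double-Blind FAS, with the sign reversed so that higher is better. Here inability does have a rule: "a z-score will be imputed using the worst observed z-score across all patient visits". Change in z-score goes into an MMRM if enough patients have data.

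Two general table rules in SAP 6.1.5 matter. Item 4 adds an Unknown or Missing row when a categorical value is not available. Item 7 makes the default percentage denominator all patients in the treatment group and analysis set.

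Protocol 9.5.6 restricts the test to patients who can walk safely, alone or with support, and has the Screening evaluation decide who can be tested.

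**The concern.** Losing the ability to complete the walk is the worst result this test can give. Protocol Section 4 describes loss of walking as part of the usual course in affected children, so the event is foreseeable. Yet it does not enter the one category meant to capture deterioration, or the mean change in seconds. The Missing row would also mix these patients with those who were never given the test and those who skipped a visit.

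The SAP does not regard inability as uninformative, because the z-score rule in the same section penalises it. One event is thus handled in two incompatible ways, and the two sets of results could tell different stories about the same arm. What is at stake is the reading of an exploratory table, not the trial's main conclusion.

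**Working it through.** **The plan's own figures.** The documents give no power or effect size for the walk test. The only design figure concerns the PKAN-ADL: "a total of 74 patients (37 in each treatment group) will provide approximately 80% power to detect a 3-point difference between groups", and "this calculation assumes a standard deviation of 4.5 points for the change from baseline scores". With 37 per group, the noncentrality is (3/4.5) × √(37/2) = 2.87 on 72 degrees of freedom. Two-sided alpha of 0.05 then gives 80.8% power, so the stated figure is reproduced. It bears on this point only through the number randomized: "Allowing for 10% attrition, a total of 82 patients will be randomized". At 1:1 that is 82/2 = 41 per arm.

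**Tracing one patient through the rules.** The patient completes the test at Baseline and is unable at Week 24.

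| Output | Rule that applies | Result |
|---|---|---|
| Average time, Week 24 | Two successful trials needed; one-trial fallback excludes inability | No value |
| Change and percent change in seconds | Need the Week 24 time | No value |
| Improvement / no change / worsening | SAP 6.1.5 item 4 | Unknown or Missing |
| z-score, Week 24 | Worst observed z-score | Imputed; normally a fall |

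**Size in the status table.** If *w* patients have a slower time and *k* lose the ability, the table shows *w*/N worsening where (*w* + *k*)/N is the true share. The shortfall is *k*/N. The documents give neither *w* nor *k*. Take N = 41 (assuming every randomized patient is in the FAS) and *w* = 10 (assumed):

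- *k* = 1: 10/41 = 24% shown, 11/41 = 27% true
- *k* = 3: 10/41 = 24% shown, 13/41 = 32% true
- *k* = 5: 10/41 = 24% shown, 15/41 = 37% true

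**Can the two sets of results diverge?** Take an invented arm of eight Baseline walkers with times of 6, 8, 10, 12, 15, 20, 18 and 25 s. At Week 24 the first six take 6, 7, 10, 11, 15 and 19 s, and the last two are unable.

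- Seconds: six changes (0, −1, 0, −1, 0, −1), mean −3/6 = −0.5 s, which is an improvement. Three improved, three unchanged, none worse, two missing.
- z-score: Baseline mean 14.25 s, SD 6.475 s. The worst z is −(25 − 14.25)/6.475 = −1.660. The 18 s patient goes from −0.579 to −1.660, a change of −1.081. The 25 s patient already holds the worst value, so the change is 0. Each one-second gain is worth 1/6.475 = 0.154. The mean is (3 × 0.154 − 1.081)/8 = −0.077, which is a deterioration.

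So the two can point in opposite directions. The example shows that this is possible, not how likely it is.

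**The case against.** The case for leaving the text alone has real force.

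- **Loss of walking is visible elsewhere.** SAP 4.10.3.5 tabulates failed trials, assistive devices and changes in the level of assistance. SAP 4.10.3.4 tabulates FIM locomotion at Baseline and Week 24. The PKAN-ADL includes walking and has item-level status tables (SAP 4.10.1). The z-score penalises most patients who lose the ability. This stands and limits the importance, but none of it corrects the status table.
- **The consequence is small.** SAP 4.10.4 places this endpoint outside the gatekeeping, and no test is specified on the seconds tables. This also stands.
- **The event may be rare in 24 weeks.** Protocol Section 4 speaks of 10 to 15 years from onset, and support is allowed during the test. Any number of losses is an assumption.

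Three stronger readings are tempting, and the documents do not support them.

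1. A reader might infer that the percentage base shrinks to patients with times, so that an arm losing walkers gains further. SAP 6.1.5 item 7 keeps the whole arm as the default denominator; only the numerator is affected.
2. A reader might infer that patients who never walk receive the same worst z-score at every visit, a change of exactly 0, and so dilute the treatment difference by their share. The imputation wording permits this, but the section opens with patients able to attempt the test, and Protocol 9.5.6 screens the others out. It is an ambiguity, and the share of such patients is not given.
3. A reader might conclude that z-score analyses should be limited to patients who completed the test at Baseline. That would discard anyone who passed Screening, failed at Baseline and later completed the test, so losses would count and gains would not.

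**Conclusion.** The point holds as a minor correction. Followed as written, the seconds-based status table and improvement bands leave out Baseline walkers who become unable, and the undercount of worsening equals their number. In the illustration with 3 such patients this is 24% shown against 32% true, about 7 percentage points (3/41). That rests on assumed counts, on 41 per arm in the FAS, and on the default denominator. The omission follows from the lack of a rule, not from a stated exclusion.

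As to the mean in seconds, these patients are absent from it. Whether that flatters an arm depends on whether the slowest walkers are the ones lost, which is plausible but not documented. The scope of the z-score imputation needs a clarifying phrase; it is not a demonstrated bias. The primary and secondary analyses, the significance level and the sample size are unaffected.

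**What to change.** In SAP 4.10.3.5:

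1. For patients who completed the walk test at Baseline, classify any later visit at which they cannot complete it through inability as worsening in the status table and as <0% in the percent-improvement bands. Visits missed for other reasons stay under Unknown or Missing.
2. Footnote the seconds summaries, by arm and visit, with the number of patients unable to complete the test.
3. State that the worst-z imputation applies to patients who passed the Screening evaluation for the walk test (Protocol 9.5.6). Patients never given the test then receive no constant z-score, and patients who fail at Baseline but complete the test later keep their gain.

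The cost is SAP wording and a small programming change. Inability already has to be identified for the one-trial rule, the z-score imputation and the failed-trial table, so no new data collection should be needed. The wording should be settled before unblinding, so that the choice does not depend on the results.

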DDK is a common component of the cranial nerve examination used by neurologists and speech language pathologist to assess oral motor function. Both the AMR and SMR assessments require the participant to produce a target syllable (eg, puh-puh-puh) or syllable sequence (eg, puh-tuh-kuh) as fast and accurately as possible within one breath. Because the syllables are produced at a rapid rate, the task is intended to be physiologically demanding, thus testing the physiologic capacity of the oral motor system. Performance is quantified using 2 scores: repetition rate in seconds (also called DDK rate), and repetition count (ie, the number of repetitions produced in one breath). Normative data for DDK is widely published ([Kent, 1987](#)), and DDK has been shown to be a strong indicator of oromotor impairments due to amyotrophic lateral sclerosis ([Dworkin, 1980](#); [Rong, 2016](#)) and other neurologic conditions including ataxia ([Sidtis, 2010](#)), Parkinson's disease ([Tjaden, 2003](#)), multiple sclerosis ([Tjaden, 2003](#)) and traumatic brain injury ([Wang, 2004](#)).

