improvement (i.e. increase) in rescaled total score from baseline (i.e., <0%, =0% >0%, $\geq 10\%$, $\geq 20\%$, $\geq 30\%$, $\geq 40\%$, $\geq 50\%$), categories for rescaled total score status (improvement, no change, or worsening) will be presented for each module. This table will be repeated using age group (pediatric, adult) as a subgroup.

Chi-squared tests will be performed for each module at each post-baseline assessment to determine treatment differences between the percentages of patients who had a re-scaled total score indicating improvement, no change, or worsening. Proportions, with estimated 95% CI, will be reported for each treatment group, along with a p-value corresponding to the treatment comparison.

In addition, the change in Neuro-QoL assessments (rescaled score for each module) from baseline to the Week 12 and final (Week 24) visit will be evaluated at each time point using an MMRM, similar to the one described for the primary endpoint. The model will be run using the Double-Blind FAS.

A by-patient listing will be provided, which presents the raw responses to all items in the Neuro-QOL assessment, along with the rescaled total score for each module, across all assessments in the double-blind and open-label periods for patients in the Double-Blind FAS.

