4.10.3.3.2 Euro-Qol

The EQ-5D-3L (for adult patients) measures 5 dimensions (mobility, self-care, usual activities, pain/discomfort and anxiety/depression), each rated at 3 levels: 1=no problems, 2=some problems, 3=extreme problems. The scale also records the patient's self-rated health on a visual analogue scale (VAS) from 0=the worst health you can imagine, to 100=the best health you can imagine. The EQ5DY (for pediatric patients) measures the same 5 dimensions on a similar 3-point scale and uses the same VAS for the patient to self-rate health.

Frequency counts of the change from baseline score across each of the 5 dimensions, as well as shift from baseline, will be presented for each visit during the double-blind period. Categories for change from baseline dimension score (i.e., >0 , $=0$, <0 , ≤ -1), and categories for dimension score status (improvement, no change, or worsening) will be presented at Week 24, as well. These tables will be repeated using age group (pediatric, adult) as a subgroup.

Furthermore, each patient's 5-digit EQ-5D state will be transformed into a single EQ-5DTM index score by following the algorithm, or value set, specified for his or her relevant country. These value sets are derived based off surveys conducted in representative samples of the given countries. The value set is anchored at 0=dead and 1=full health. The EURO-QOL group provides the value set for performing these calculations, and one such reference table can be found in [Janssen \(2014\)](#). If there are any

missing data across the 5 dimensions at a given visit, then the index score cannot be validly calculated and is considered missing.

Descriptive statistics of the EQ-5D™ index score will be presented for patients in the Double-Blind FAS at each visit of the double blind period, including absolute change from baseline. Categories for percent improvement (i.e., increase) in EQ-5D™ index score from baseline (i.e., <0%, =0% >0%, ≥10%, ≥20%, ≥30%, ≥40%, ≥50%), and categories EQ-5D™ index score status (improvement, no change, or worsening) will be presented. In addition, descriptive statistics of the patient's self-rated health on the VAS, as well as absolute change from baseline, will be presented for each visit of the double-blind period. This table will be repeated using age group (pediatric, adult) as a subgroup.

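### SAP 4.10.3.5 defines improvement in the DDK speech rates as a decrease, although the rates are repetitions per second, so the percent-improvement bands are reversed as written

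*SAP*

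**What the plan says.** The Speech part of SAP 4.10.3.5 sets up four DDK scores: three alternating motion rates (AMR), one per syllable, and one sequential motion rate (SMR). "The AMR will be derived as the number of repetitions over the duration (in seconds"), and the SMR is derived in the same way. The patient is asked to go at maximum speed within one breath.

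The same section then asks for "Categories for percent improvement (i.e., decrease) in AMR/SMR", with bands <0%, =0%, >0%, ≥10%, ≥20%, ≥30%, ≥40% and ≥50%. It adds that "categories for AMR/SMR status (improvement, no change, or worsening) will be presented", without saying which direction counts as improvement. Both displays are repeated by age group.

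For the other exploratory scores on which higher is better, the SAP uses the opposite label:

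- Neuro-QoL (4.10.3.3.1): "improvement (i.e. increase) in rescaled total score from baseline"
- EQ-5D index (4.10.3.3.2): "Categories for percent improvement (i.e., increase) in" the index score
- FIM (4.10.3.4): "categories for percent improvement (i.e., increase) in" the total score

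Protocol 9.5.6 describes the DDK score as "repetition rate in seconds (also called DDK rate") and gives no formula.

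**The concern.** A rate of repetitions per second rises when speech gets faster, so calling a fall an improvement turns the bands round. If the text is programmed as it stands, patients whose speech slows would be counted as improved in the interim clinical study report, and those whose speech quickens would sit in the <0% band. If the drug had a real effect on DDK speed, this table would point the opposite way from the DDK ANCOVA reported beside it. The status categories carry no direction of their own. They would be reversed too if the programmer took the only direction the section gives.

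**Working it through.** The documents give no figure to reproduce here; the check is one of direction.

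**Inputs**

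- Score = repetitions / seconds (SAP 4.10.3.5, both AMR and SMR).
- Percent change = 100 × (post − baseline) / baseline (SAP 4.10.1).
- Improvement as written = −(percent change), because the label says decrease. Improvement under the correction = +(percent change).
- Example rates are assumed: a baseline of 20 repetitions in 5 s = 4.0 per second. The sign result holds for any positive baseline.

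**Placement of individual patients**

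| Change (repetitions/s) | Percent change | Bands as written | Bands if improvement is an increase |
|---|---|---|---|
| 4.0 to 5.0 | 100 × (5 − 4)/4 = +25% | <0% | >0%, ≥10%, ≥20% |
| 4.0 to 3.0 | 100 × (3 − 4)/4 = −25% | >0%, ≥10%, ≥20% | <0% |
| 4.0 to 4.0 | 0% | =0% | =0% |

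Only the =0% band comes out the same under both rules.

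**Consistency across the SAP.** The label is *decrease* for PKAN-ADL (4.10.1), UPDRS Part III (4.10.2), BAD (4.10.3.2) and the 25-foot walk in seconds (4.10.3.5), where lower is better. It is *increase* for Neuro-QoL, the EQ-5D index and FIM, where higher is better. AMR/SMR is the only one that does not match its scale.

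**Could the score be a time?** Decrease would be right for seconds per repetition: 4.0 to 5.0 repetitions/s is 0.25 to 0.20 s per repetition, a change of −20%. That is not the SAP's formula. The unit also matters at the band edges. A change from 4.0 to 4.4 is +10.0% in repetitions per second, which reaches the ≥10% band. In seconds per repetition it is 100 × (4.0/4.4 − 1) = −9.1%, which does not.

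**Number of displays.** Week 24 is the only post-baseline DDK visit in the double-blind period, so there are 4 scores × 3 groupings (overall, pediatric, adult) = 12 sets of bands.

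**Illustration at group level.** The documents give no DDK mean or SD, so these values are assumed: percent change normal, SD 20%, mean 0% on placebo and +10% on active. For the ≥10% improvement band:

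- Correct rule, P(change ≥ +10): active Φ(0) = 50.0%, placebo Φ(−0.5) = 30.9%, difference +19.1 points.
- As written, P(change ≤ −10): active Φ(−1.0) = 15.9%, placebo Φ(−0.5) = 30.9%, difference −15.0 points.

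Over active means of 5, 10 and 15% and SDs of 15, 20 and 30%, the correct difference runs from +6.4 to +37.8 points and the as-written difference from −6.1 to −20.5.

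**The case against.** The strongest reply is that this is a wording slip with little reach. The 25-foot walk text earlier in the same section uses the same label correctly for a time in seconds, so carry-over is a plausible origin, though that is inference. A careful programmer might correct it unprompted. The mock-ups mentioned in SAP 6.2 are not available and may already be right. DDK is one of several exploratory measures (SAP 4.10.4), and the reversal could be detected: the section also reports signed absolute and percent change and the ANCOVA difference with its confidence interval, and provides a listing "which presents the duration, repetitions, and repetition rates for the AMR and SMR". All of this stands. It limits the consequence to what could happen if the text is followed, and it keeps the point minor. It does not make the text right.

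Two further objections are fair. The group-level percentages rest wholly on assumed values and say nothing about this trial; the individual ±25% examples prove the point without them. And the protocol's phrase about seconds is loose wording rather than a competing formula. It still calls the score a rate and asks for maximum speed, so it neither overrides the SAP's derivation nor has to be changed to repair the bands. Under Protocol 13.3 any protocol change goes through an amendment signed by the investigator and approved by the IRB/IEC, which is too much for this alone.

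**Conclusion.** The concern holds, and it is minor. SAP 4.10.3.5 defines a score on which higher is better and labels a fall in it as improvement; nothing elsewhere in the documents cures this. As written, every non-zero change falls on the wrong side of zero in the percent-improvement bands of all four DDK scores. The status categories are ambiguous rather than demonstrably wrong.

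The reversal depends only on the SAP's own formula and a positive baseline rate. Its appearance in the report depends on the text being programmed literally, and a visible disagreement with the ANCOVA depends on there being a treatment effect. The DDK ANCOVA, the absolute and percent change summaries, the repetition counts, the by-patient listing and the primary and secondary tests are unaffected.

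**What to change.** In SAP 4.10.3.5, change the AMR/SMR label from decrease to increase. Add one sentence stating that, for all four DDK scores, a rise from baseline is improvement and a fall is worsening in the status categories. Check the AMR/SMR mock-ups and programming specifications against the corrected text.

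At the next protocol amendment made for other reasons, align the unit in Protocol 9.5.6 with repetitions per second. This is tidying and the SAP correction need not wait for it.

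The cost is one word and one sentence in the SAP and a check of the mock-ups. No new data or analyses are needed.
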